7.2 SUBJECT DISCONTINUATION/WITHDRAWAL FROM THE STUDY

Subjects are free to withdraw from participation in the study at any time upon request.

An investigator may discontinue or withdraw a subject from the study for the following reasons:

- If the subject meets an exclusion criterion (either newly developed or not previously recognized) that precludes further study participation
- Subject is unable to do Field Test 1 and/or 2 under real-life conditions due to quarantine or social distancing due to COVID-19 pandemic.

The reason for subject discontinuation or withdrawal from the study will be recorded on the Study completion Case Report Form (eCRF). Subjects who signed the ICF and are randomized but do not receive the study intervention may be replaced. Subjects who signed the ICF, and are randomized and receive the study intervention, and subsequently withdraw, or are withdrawn or discontinued from the study, will be replaced if the minimum number of 24 subjects has yet to be enrolled.

All data is collected during use of the investigational device. In case a patient is withdrawn from the study there is no further data collection needed, except in the case the patient would report an adverse event which would be seen as at least possibly related to the treatment with the device. In this case the patient will be followed up until the event is resolved.

Data collected before withdrawal of consent will be kept in the study.

7.3 LOST TO FOLLOW-UP

A subject will be considered lost to follow-up if he or she fails to return for scheduled visits and is unable to be contacted by the study site staff.

The following actions must be taken if a subject fails to return to the clinic for a required study visit:

- The site will attempt to contact the subject and reschedule the missed visit and counsel the subject on the importance of maintaining the assigned visit schedule and ascertain if the subject wishes to and/or should continue in the study.
- Before a subject is deemed lost to follow-up, the investigator or designee will make every effort to regain contact with the subject (where possible, 3 telephone calls and, if necessary, a certified letter to the subject's last known mailing address or local equivalent methods). These contact attempts should be documented in the subject's medical record or study file.

Should the subject continue to be unreachable, he or she will be considered to have withdrawn from the study with a primary reason of lost to follow-up.

8 STUDY ASSESSMENTS AND PROCEDURES

8.1 EFFECTIVENESS ASSESSMENTS

Data are collected via questionnaires, laboratory speech testing and EMA surveys during field use. An overview is given below in Table 4.

Stage	Intervention	Method
-------	--------------	--------

Screening	Otoscopy Tympanometry Audiometry	Otoscope, tympanometer and standard audiometer performed by HCP.
	Hearing in Noise Question	HCP asks subject: Do you have trouble hearing in noise? Y/N
	Self-Perceived Hearing Loss questionnaire	HCP asks subject to describe their hearing loss on a 4-point scale: 
1. No Trouble2. A little trouble3. A lot of trouble4. Cannot hear
Visit 1	Questionnaires for primary and secondary endpoints on effectiveness	
 • APHAB The APHAB inventory yields scores for speech communication in quiet, reverberant, and noisy environments, and also measures aversiveness of loud sounds. • SSQ-12 The SSQ-12 includes the factors speech hearing, spatial hearing, qualities of hearing, and listening effort. 
➔ Both completed for unaided condition (irrespective of hearing aid experience)

	Randomized Vibe SF or Silk 1X HCP fit hearing aids: Bilateral Hearing Aid fitting	EasyFit web application (Vibe SF strategy) performed by subject. Connexx Fitting Software NAL-NL2, verified with probe-mic REM (Silk 1X HCP fit strategy) performed by HCP.
	Fine-tuning	For Vibe SF strategy, with fine-tuning dialog on EasyFit web application done independently by subject. For Silk 1X HCP fit, fine-tuning with HCP as is standard clinical practice.
Field Test 1	Fine-tuning Situation tuning	For Vibe SF strategy, with fine-tuning dialog and situation tuning is performed with the EasyFit web application by the subject. For Silk 1X HCP fit strategy, fine-tuning appointment with HCP if necessary due to persistent need for fine-tuning that cannot be resolved with the situation tuning using the Signia App.
	Follow-up to ensure EMA survey data capture	Phone call from investigational staff approximately 3+3 days after visit to ensure that daily EMA surveys are being completed; any questions related to data collection may be answered. Questions regarding the hearing aids may NOT be answered and subject will be reminded to refer to the study information provided to them at Visit 1.
	Sound quality, speech understanding and hearing aid satisfaction ratings for secondary endpoint on effectiveness	Subjects will be asked via their study smartphones to give short ratings of sound quality and speech understanding satisfaction in their current listening situation. This EMA is a methodology involving repeated surveys to collect data describing subjects' current or very recent experiences in their real-life conditions.
Visit 2 (only cross-over design)	Questionnaires for primary and secondary endpoint on effectiveness	
 • APHAB • SSQ-12 
➔ Both completed Aided (Field Test 1 device) and if necessary, assistance given by HCP

	Field Test 1 Vibe SF Strategy or Silk 1X HCP fit hearing aids put in storage	Each subject's Vibe SF or Silk 1X HCP fit hearing aids of the Field Test 1 will be blind coded and stored so that the speech test at the final visit (Visit 3) may be done with the exact settings used during the Field Test 1 (i.e., including fine-tuning).
	Cross Over Vibe SF or Silk 1X HCP fit hearing aids: Bilateral Hearing Aid fitting	EasyFit web application (Vibe SF strategy) performed by subject. Connexx Fitting Software NAL-NL2, verified with probe-mic REM (Silk 1X HCP fit strategy) performed by HCP. (only cross-over design)
	Fine-tuning	For Vibe SF strategy, with fine-tuning dialog on EasyFit web application done independently by subject. For Silk 1X HCP fit, fine-tuning with HCP as is standard clinical practice. (only cross-over design)
Visit 2 (only parallel-arm design)	Questionnaires for primary and secondary endpoint on effectiveness	
 • APHAB • SSQ-12 
➔ Both completed Aided (Field Test 1 device) and if necessary, assistance given by HCP

	Speech Test for secondary endpoint on effectiveness	
 • QuickSIN 
➔ Unaided ➔ Aided (Field Test 1 device)
 
A speech test is included to give objective data on speech understanding with the Field Test 1 hearing aids.

	Fitting verification of "final fit"	REM of Field Test 1 device for gain comparison
Washout Period (only cross-over design)	5 day + 2-day period of not wearing any study devices	Upon completing Visit 2, the site will collect the hearing aids fitted at Visit 2, store them and send them out upon completing the 5-day washout period.
Field Test 2 (only cross-over design)	See Field Test 1	See Field Test 1
Visit 3 (only cross-over design)	Questionnaires for primary and secondary endpoint on effectiveness	
 • APHAB • SSQ12 
➔ Both completed Aided (Field Test 2 device) and if necessary, assistance given by HCP

	Speech Test for secondary endpoint on effectiveness	
 • QuickSIN 
➔ Unaided ➔ Aided (device order randomized and double-blinded)
 
A speech test is included to give objective data on speech understanding with the Vibe SF and Silk 1X HCP fit hearing aids.
 
Reasons to do speech testing for all three conditions at the end of the study:
 
 1. Otherwise, not able to do perform double-blinded. 2. The cross-over design minimizes ordering bias effects.

	Fitting verification of “final fit”	REM of both fitting strategies (Vibe SF/HCP fit) for gain comparison, device order randomized and double-blinded.
	Fitting Preference	Subjects will be asked to respond to the following question on a 5-point Likert scale: Based on your listening experiences regarding speech understanding, sound quality and naturalness for both products, if you could keep one pair of these hearing aids, which would you choose?

Table 4. Overview of test tools utilized

8.1.1 SCREENING

Potential subjects will be recruited locally by outreach at the investigator sites, local advertisements, social media advertisements and professional recruiting service. Initial phone/electronic screening will include the question of whether he/she has trouble hearing in noise. If no, they will be excluded. Those remaining will then be asked to rate on a scale of 1-4 her/his perceived hearing loss (no trouble, a little trouble, a lot of trouble, and cannot hear). Listeners at the two extremes will be excluded.

Listeners with appropriate responses are provided an overview of the study intent (subject information) and invited into the clinic to be assessed for eligibility, according to inclusion and exclusion criteria, as described in Section 5.1 and 5.2.

The session begins with otoscopy, tympanometry and a standard audiometric evaluation consisting of air and bone conduction thresholds for each ear. If it is determined they have mild-to-moderate hearing impairment and fulfil all inclusion criteria they will be given study subject information and asked for their voluntary informed consent to participate in the clinical study.

If at this time a subject is identified with significant asymmetries in hearing, the HCP will refer them to an audiologist and/or ENT for follow-up and subject will be excluded from the study (screen failure).

8.1.2 VISIT 1

Subjects complete two questionnaires concerning unaided hearing¹: the APHAB and SSQ-12. The subjects can ask questions, and the HCP or assistant reads through the filled-out questionnaires with the subject to make sure everything is understood and filled out appropriately.

¹ Participants that have experience with hearing aids are nonetheless asked to fill out the questionnaires as they would *without* the use of their hearing aids in order to have the same baseline for all participants.

Investigational staff complete the randomization process to determine which pair of study hearing aids the subject will receive.

Hearing aid fitting is conducted in a quiet dedicated hearing aid fitting and counselling room.

The subjects starting with the *Vibe SF* strategy, independently fit their *Vibe SF* hearing aids bilaterally themselves using the *EasyFit* web application on the study smartphone provided to them. They are provided with *Vibe SF* Safety and Maintenance Information, Quick-Start Guide and a Quick-Start Card. The HCP will not interfere or assist subject in fitting their hearing aids.

For the subjects starting with the HCP fit strategy, an HCP fits the *Silk 1X* hearing aids bilaterally using the *Connexx* fitting software to NAL-NL2 validated prescription target, probe-mic REM and conduct fine-tuning as is standard clinical practice.

All subjects are given a user manual for the hearing aids, along with instructions by the HCP or research assistant on how to use the EMA app and study smartphone. Subjects starting with the *Silk 1X* (HCP fit strategy) will be provided counselling on the use of the *Silk 1X* hearing aids and *Signia App* (remote-control smartphone app for situation tuning).

The *EasyFit* web application guides the user through the SF procedure as well as the fine-tuning and volume control functionality. Subjects who start using the *Silk 1X* HCP fit strategy hearing aids will receive instructional material on how to use the *Signia App* for situation tuning as per standard of care.

Subjects in both groups are instructed to listen to as many listening environments as possible and enter their sound quality, speech understanding and hearing aid satisfaction ratings when randomly prompted by the clinical study smartphone, and subjects may at any time self-enter a rating. The investigational staff will practice with the subjects until they have observed that the subject is able to successfully enter their sound quality, speech understanding and hearing aid satisfaction EMA ratings without any assistance from the investigational staff.

Subjects are asked to report any ADEs occurring during field use.

8.1.3 FIELD TEST 1

All subjects wear their first pair of study hearing aids for two weeks. Since the investigation is designed as a cross-over design in order to be able to do within-subject comparisons, a two-week period was chosen to allow for acclimatization and fine-tuning but not prolong the field test to an extent where it is likely that subjects would drop out of the study or be less motivated in the second field test.

The EMA rating questions on subject's sound quality, speech understanding and hearing aid satisfaction is filled out in various listening conditions daily. The EMA consists of a short survey that is triggered randomly four times during the entire day and may also be entered at any time the subject wants to enter a rating.

The EMA survey comprises of four single/multiple choice questions (or three, if the situation does not involve speech) which are:

1. Current situation,
2. Sound quality,

3. Speech understanding,
4. Satisfaction

If the timing is inconvenient (e.g., driving a car), the subject can delay the response to the survey (reminder is given to not delay the response unduly, e.g., for more than 1 hour).

Phone calls (approximately after 3 days +3 days field testing) are scheduled with investigational staff. These calls are intended to ensure that all EMA data collection tools are functioning and subjects are reminded to report any adverse device effects (ADE) occurring during field use. The subject also has the possibility to call/e-mail the investigation staff when needed; however, to mitigate the potential for introducing bias through counselling of the self-fit group, any questions about the *Vibe SF* fitting strategy or how to use the device will not be answered by the investigational staff.

For the subjects who start in the HCP fit strategy group, based on complaints the subjects have about sound quality, the audiologist/HCP is able to invite the subject for an in-person fine-tuning visit and adjust the fitting on their *Silk 1X* as in a real-life HCP fitting (standard clinical care).

Subjects are asked to report any ADEs occurring during field use.

All communication with the HCP and/or investigation staff during the field tests will be documented and saved.

8.1.4 VISIT 2

Subjects return to the clinic after approximately two weeks Field Test 1 use. Subjects complete two questionnaires: the APHAB and the SSQ-12, to reflect their hearing experience aided with the Field Test 1 hearing aids. An HCP or assistant reads through the filled-out questionnaires with the subject to make sure everything is understood and filled out sufficiently.

Subjects are asked to report any ADEs occurring during field use.

Cross-over design:

The Field Test 1 HCP fit strategy subjects now cross over to the *Vibe SF* strategy group. Subjects independently fit their *Vibe SF* hearing aids bilaterally themselves using the *EasyFit* web application on the study smartphone. They are provided with the *Vibe SF* Safety and Maintenance Information, Quick-Start Guide and Quick-Start Card (see Appendix II). The HCP will not interfere or assist the subject with the self-fitting.

The Field Test 1 *Vibe SF* strategy subjects now cross over to HCP fit strategy group. An HCP fits the *Silk 1X* hearing aids bilaterally using the *Connexx* fitting software, to NAL-NL2 validated prescription target, probe-mic REM and conducts fine-tuning as is standard clinical practice.

The hearing aids of the Field Test 1 are stored without altering the settings to be used in the REM and speech tests of the final visit (Visit 3).

Parallel-arm design:

12 subjects: The Field Test 1 Vibe SF strategy subjects now cross over to HCP fit strategy group. An HCP fits the Silk 1X hearing aids bilaterally using the Connexx fitting software, to NAL-NL2 validated prescription target, probe-mic REM and conducts fine-tuning as is standard clinical practice.

The hearing aids of the Field Test 1 are stored without altering the settings to be used in the REM and speech tests of the final visit (Visit 3).

38 subjects: This is their final visit. The subjects will not cross over to the other fitting strategy.

Effectiveness is measured with QuickSIN in an unaided condition and aided with Field Test 1 fit hearing aids in a sound attenuated booth. REM will be conducted on Field Test 1 hearing aids.

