Secondary Preference Objective:

Fitting strategy (*Vibe SF* or HCP fit) preference reported by the subject.

Secondary Safety Objective:

To estimate the rate of adverse device effects (ADEs) when the subject is using the *Vibe SF* hearing aids.

Endpoints:**Primary Effectiveness Endpoint:**

Differences in the benefit scores on each of the three communication subscales as captured by the Abbreviated Profile of Hearing Aid Benefit (APHAB) after wearing each *Vibe SF* / Silk 1X HCP fit hearing aids for 14 days. For each subject, the endpoints are the individual 3 communication subscale differences between the HCP fit subscale (benefit) score and SF subscale (benefit) score:

- $\Delta EC(benefit)_{HCP\ fit} - \Delta EC(benefit)_{SF}$
- $\Delta BN(benefit)_{HCP\ fit} - \Delta BN(benefit)_{SF}$
- $\Delta RV(benefit)_{HCP\ fit} - \Delta RV(benefit)_{SF}$

Secondary Hearing Aid Benefit Endpoints:

1. The subject's sound quality, speech understanding and hearing aid satisfaction Ecological Momentary Assessment (EMA) ratings measured repeatedly under real-life conditions,
2. Speech-in-noise recognition performance as measured by the Quick Speech-In-Noise test (QuickSIN),
3. Hearing disability resulting from hearing loss quantified by the short form of the Speech, Spatial, and Qualities of Hearing Scale for clinical use: the SSQ-12 questionnaire.

Secondary Gain Selection Endpoint:

Individual frequency-specific gain comparison for the two different fitting strategies (*Vibe SF* and HCP fit) for each ear as measured with probe-mic real-ear measures (REM).

Secondary Preference Endpoint:

Fitting preference *Vibe SF* or HCP fit strategy. Subjects are asked which of the hearing aids they would prefer to keep using a 5-point Likert scale.

Secondary Safety Endpoint:

The number of adverse device effects (ADEs) in the time period when the subject is using the *Vibe SF* hearing aids.

Population: A minimum of 28 US subjects, within the age of 18 years and older, inexperienced or experienced hearing aid users with perceived mild-to-moderate hearing impairment. Potential subjects will be screened to confirm their bilateral sensorineural hearing loss.

Description of Sites/Facilities Enrolling Subjects: A single US University hearing aid research clinic. Potential subjects will be recruited locally by outreach at the investigator sites, local advertisements, social media advertisements and if needed professional recruiting service.

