6.3 MEASURES TO MINIMIZE BIAS: RANDOMIZED TREATMENT ORDER AND BLINDING

To avoid order effect of evaluating *Vibe SF* strategy and *Silk 1X HCP fit* strategy, a balanced randomization list will be generated using approved statistical software. A computer-generated pseudo-random-number list will be used for assigning the treatment order. Assignments will be made either by sealed envelope or provided real-time on the sponsor's electronic database capture (EDC) website on a protected page. New hearing-aid users and experienced hearing-aid users will be distributed evenly in the two randomized groups.

Cross-Over Design: Minimum 12, Maximum 28 subjects

At the final visit (Visit 3), the order of testing the experimental and reference devices will be randomized for the QuickSIN and REM lab tests. Randomization will be handled by a designated person not otherwise involved in the study.

During each of the following performance measures, QuickSIN and REM, at Visit 3 when the subject is using the *Vibe SF* and *Silk 1X HCP fit* hearing aids, the identity of the *Vibe SF* and *Silk 1X* will be double blinded to the subject and assessor. An assistant other than the HCP will help secure double blinding during the lab assessments by handling the blinding codes, storing, retrieving and presenting the appropriate hearing aids for evaluation.

During Field Tests 1 and 2 use, blinding is not possible since the option of self-finetuning or finetuning visits to the HCP reveals the device under investigation.

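### At Visits 2 and 3 an HCP, possibly the one who fitted the subject's Silk 1X, may review and assist with the unblinded primary questionnaire; assign this to an assistant who did no fitting

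*Combined protocol and SAP*

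**What the plan says.** Sections 1.1 and 3 make the three APHAB communication subscales the primary endpoint, and section 9.1.2 confirms that no secondary objective carries a hypothesis test. Section 6.3 accepts that the field tests cannot be blinded.

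Sections 8.1.4 (Visit 2) and 8.1.7 (Visit 3) have the subject complete the aided APHAB and SSQ-12, and then: "An HCP or assistant reads through the filled-out questionnaires with the subject", as a check on understanding and completeness. Table 4 in section 8.1 describes the same step differently. For Visit 2 it reads "Both completed Aided (Field Test 1 device) and if necessary, assistance given by HCP", and for Visit 3 "Both completed Aided (Field Test 2 device) and if necessary, assistance given by HCP". No assistant is mentioned there.

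The HCP also fits and fine-tunes the Silk 1X (8.1.2, 8.1.4) and may call the subject in for further fine-tuning during the field test (8.1.3).

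The plan limits staff influence elsewhere. For QuickSIN and REM at Visit 3, section 6.3 provides that "An assistant other than the HCP will help secure double blinding during the lab assessments by handling the blinding codes". Section 6.1.3 keeps the HCP out of randomization, coding and retrieval of devices for Visit 3. Section 8.1.3 has staff decline questions about Vibe SF so that counselling does not introduce bias.

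**The concern.** The endpoint that decides the trial is a subject's opinion of a device whose identity the subject knows. Going over the answers face to face with the professional who fitted one of the two devices can change them, through courtesy, reassurance or reinterpretation of items. The plan recognises this kind of risk for descriptive secondary measures and for field-test telephone calls, but has no matching safeguard for the APHAB. It gives no script, no limit on changing answers and no log of changes; the documentation rule in 8.1.3 covers communication during the field tests, not the visits.

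The exposure is also not the same for the two devices, because only the Silk 1X has a professional fitter. An influence that differs by device does not cancel in the HCP-minus-SF difference. It moves the estimate and its confidence bound by the same amount.

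**Working it through.** **1. Who may touch the primary outcome, compared with the other measures**

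| Measure | Role in the analysis | Staff rule |
|---|---|---|
| Aided APHAB, Visits 2 and 3 (8.1.4, 8.1.7) | Primary, tested | HCP or assistant reads it through |
| Same step in Table 4 | Primary, tested | HCP assists if needed; no assistant named |
| QuickSIN and REM, Visit 3 (6.3) | Secondary, descriptive | Assistant other than the HCP handles codes and devices |
| Field-test calls (8.1.3) | Support | Vibe SF questions not answered |

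The strictest rules apply to the descriptive measures, and Table 4 disagrees with the text on who helps.

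**2. When the reviewer could be the fitter**

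| Sequence | Visit 2 APHAB describes | Visit 3 APHAB describes |
|---|---|---|
| HCP fit first | Silk 1X; the reviewer could be its fitter | Vibe SF; the reviewer could have fitted the earlier Silk 1X |
| Vibe SF first | Vibe SF; no HCP has yet fitted a study aid (8.1.4 describes the APHAB before the cross-over fitting) | Silk 1X; the reviewer could be its fitter |

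In the parallel-arm design only the Visit 2 column applies to the 38 added subjects, so the exposure falls in the HCP-fit arm only.

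Visit 1 is different. Section 8.1.2 places the unaided APHAB before randomization and fitting, and the section 9.2 footnote notes that this baseline cancels in the cross-over comparison.

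**3. The plan's own sample-size figure**

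Inputs from section 9.2: margins 26 (EC), 27 (BN) and 28 (RV); SD of the difference 34.4, 36.2 and 36.1 (as in the power table); one-sided alpha 0.05; true difference 0.

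Formula: power = P(T > t with 0.95 probability below it, n−1 df), where T is noncentral t with noncentrality margin / (SD/√n).

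- EC, n = 23: 0.96892
- BN, n = 23: 0.96555
- RV, n = 22: 0.96942

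All three match the plan's table. The fix changes none of these inputs, so 23, raised to 24 and then 28, stands.

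**4. What a shift would do (illustration only)**

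The documents give no size or direction, so shifts of 2 and 5 points are assumed here, in both directions. With n = 24 the standard errors are 34.4/√24 = 7.02, 36.2/√24 = 7.39 and 36.1/√24 = 7.37.

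*Shift s against Vibe SF, true difference 0.* Noncentrality is (margin − s)/SE. The three powers are multiplied as if independent, as the plan does (0.965³ = 0.90).

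| s | EC | BN | RV | Combined |
|---|---|---|---|---|
| 0 | 97.4% | 97.1% | 97.9% | 92.7% |
| 2 | 95.3% | 94.9% | 96.2% | 87.0% |
| 5 | 89.5% | 89.3% | 91.7% | 73.3% |

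(Combined values use unrounded powers.)

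*Shift s towards Vibe SF, true difference exactly at the margin.* Noncentrality is s/SE.

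| s | EC | BN | RV |
|---|---|---|---|
| 0 | 5.0% | 5.0% | 5.0% |
| 2 | 8.6% | 8.3% | 8.4% |
| 5 | 17.0% | 16.2% | 16.2% |

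These are errors for one subscale. All three must pass, so the trial-level error cannot exceed the smallest passing probability among the three and will usually be lower.

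**The case against.** The strongest reply is that the plan already permits the better option. In 8.1.4 and 8.1.7 the subject fills in the form first, an assistant may do the read-through, and its stated purpose is to check understanding and completeness. Table 4 limits HCP help to cases of need ("if necessary, assistance given by HCP"). All of that is correct. It narrows the concern but does not remove it: the HCP is an equal choice in the text and the only one named in Table 4.

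A reader might infer four stronger things, none of which the documents support.

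- *That the fitter and the reviewer are the same person.* The text says only that an HCP fits and that an HCP or assistant reviews. It allows the overlap; it does not state it.
- *That the trial is biased towards declaring non-inferiority.* A fitter's influence on answers about his or her own fitting would more naturally favour the Silk 1X, which works against Vibe SF. Influence the other way, or towards similar answers, is possible but not described.
- *That the change costs nothing.* No staffing or cost data are given. The assistant in section 6.3 is specified for the Visit 3 laboratory tests, and assistant cover for the Visit 2 questionnaire is not described.
- *That using an assistant would blind the outcome.* No assistant is shown to be blinded at the APHAB review, the one in section 6.3 handles the codes, and the subject knows the device in any case.

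**Conclusion.** The point holds as a cheap improvement. The plan leaves an avoidable route by which the professional who fitted the comparator may take part in recording the only tested endpoint, and Table 4 conflicts with 8.1.4 and 8.1.7 on who assists.

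The size and direction of any effect are unknown. The power and error figures show only that shifts of a few points, if they occurred, would matter in either direction. They rest on the plan's SDs, zero correlation between a subject's two scores, 24 completers and assumed shifts; the combined power also assumes independent tests. They are not evidence that the result would be biased. The finding concerns procedure and does not depend on them.

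**What to change.** - In 8.1.4 and 8.1.7, and in the Visit 2 and Visit 3 rows of Table 4 (both Visit 2 versions), name one person for read-through and assistance: *an assistant who did not fit or fine-tune the subject's hearing aids*. This also removes the conflict between Table 4 and the text.
- Limit help to completeness and the meaning of items, under a short neutral script with no discussion of how the device performed.
- Log any answer changed during the read-through, with the value before and after.
- Have the subject complete the form before any contact with the HCP at that visit.

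Section 8.1.2 needs no change for this reason, since no device has been fitted when the baseline form is completed.

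Cost: protocol wording, a script and a log. An assistant is already permitted for this task, so no new role is needed, and sample size, endpoint and analysis are unchanged. The downsides are that the HCP can no longer answer questionnaire queries and that assistant time must be scheduled at Visits 2 and 3. The change removes the fitter's influence at the review; the outcome remains an unblinded self-report.
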